Data Analyses. We will evaluate potential baseline differences between groups despite random assignment, and any that exist that may relate to outcome will be used as covariates or fixed factors. Analysis will be conducted on an intent-to-treat basis, using all randomly assigned subjects. Both during treatment (baseline to post-treatment) and longer-term (month 4) efficacy will be evaluated.

Aim 1: To evaluate the feasibility and acceptability of this intervention, the proportion of parents assigned to the intervention who complete 6 sessions will be examined, as will the proportion of youth who attend the sessions. Parent and child ratings of satisfaction with the intervention will be assessed.

Aim 2: To examine the effect size of the intervention on reducing gaming, parental reports of proportion of days on which their child played games and durations of game playing will be compared between conditions, controlling for baseline indices. These are continuous measures, with missing data likely. Hierarchical linear models (HLM; Gibbons et al., 1993) will analyze differences between groups over time. These analyses have advantages over repeated measures as they estimate missing data via model parameter estimates and use real time, as opposed to scheduled time, of assessments. Analyses will be conducted for both short and long-term effects. The model will include factors representing group (using contrasts above), time, and the interaction of group by time, along with any important covariates.

Exploratory aims are to assess the effect size of the intervention on secondary outcomes including CBCL scores, family communication, psychosocial functioning and quality of life. Using similar HLM analyses as outlined above we will compare groups over time on these indices.

Power analyses. This pilot study is designed to assess feasibility and effect sizes. Twenty subjects per group are sufficient to assess effect sizes, and if medium or larger effect sizes are noted, subsequent larger scale psychotherapy development trials will be proposed to evaluate short and long-term efficacy of this intervention.

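### Aim 2 asks for control of baseline, but the group-by-time term over a baseline-to-post-treatment window is a plain difference in change, less precise than a baseline-adjusted contrast

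*Combined protocol and SAP*

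**What the plan says.** All of this stands in the Data Analyses section of the combined protocol and SAP.

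- Purpose under Aim 2: the parent-reported share of gaming days and the durations "will be compared between conditions, controlling for baseline indices".
- Model, a hierarchical linear model: "The model will include factors representing group (using contrasts above), time, and the interaction of group by time", with important covariates added. No contrasts are defined above that sentence.
- Windows: "Both during treatment (baseline to post-treatment) and longer-term (month 4) efficacy will be evaluated", and again under Aim 2, "Analyses will be conducted for both short and long-term effects".
- Baseline differences between the groups: "any that exist that may relate to outcome will be used as covariates or fixed factors".
- Population and data: "Analysis will be conducted on an intent-to-treat basis, using all randomly assigned subjects"; "These are continuous measures, with missing data likely". The model is also said to "use real time, as opposed to scheduled time, of assessments".

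The Assessments paragraph gives three time points: pre-treatment, end of treatment at about week 8, and about two months after that. Power analyses gives 20 per group and ties larger trials to effect sizes of medium size or more. The plan does not say whether baseline is an outcome, a covariate or both, and it names no standardising SD.

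**The concern.** Two statements in the plan pull apart. Controlling for baseline suggests adjustment, in which the post-treatment difference is corrected by the regression of outcome on baseline. A group-by-time term over a window that starts at baseline gives something else: the difference between arms in raw change. That is adjustment with the slope fixed at 1, whatever the true correlation.

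Aim 2 exists to produce an effect size, and the plan lets that effect size inform whether a larger trial is proposed. With 20 families per arm the estimate is imprecise under any method. A method that adds avoidable noise makes an ineffective intervention more likely to look medium by chance, and blurs a real effect, when the same data could give a tighter estimate.

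**Working it through.** **Inputs.** From the plan: 20 per arm, 40 in total (Power analyses); three assessments; an entry floor of 15 hours/week (Approach, inclusion criteria). The plan gives no power calculation, SD or correlation, so it has no figure to reproduce. Assumed: equal variances at both visits (SD = 1), complete data, baseline-to-follow-up correlation ρ of 0.3, 0.5, 0.7 or 0.8, and medium taken as 0.5 SD.

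**Step 1: what the named term estimates.** In a two-assessment fit with free baseline means, write Y(i,t) = a + b·group + c·time + d·group·time + u(i) + e(i,t). Each family's change is Y(i,1) − Y(i,0) = c + d·group + noise, so d is estimated by the mean change in one arm minus the mean change in the other.

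**Step 2: add baseline as a main-effect covariate.** Its value is the same at both of a family's visits, so it cancels from Y(i,1) − Y(i,0). With complete data and common visit times, the estimate of d is unchanged; a numerical check agreed to within rounding error. If actual visit times vary, the two estimates need no longer match exactly.

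**Step 3: variances of the contrast at one visit, with n = 20.**

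- Post-treatment only, baseline ignored: 2/n = 0.100.
- Difference in change: 2(1 − ρ) × 2/n.
- Baseline-adjusted: (1 − ρ²) × 2/n × (1 + 1/36), where 36 = 40 − 4 allows for estimating the slope.
- Ratio of change to adjusted: [2/(1 + ρ)] × 36/37.

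At ρ = 0.3: change 2 × 0.7 × 0.1 = 0.140; adjusted 0.91 × 0.1 × 37/36 = 0.0935; ratio 1.50.

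| ρ | SE, post only | SE, change | SE, adjusted | Variance ratio, change/adjusted | 40 families worth (40/ratio) |
|---|---|---|---|---|---|
| 0.3 | 0.316 | 0.374 | 0.306 | 1.50 | 27 |
| 0.5 | 0.316 | 0.316 | 0.278 | 1.30 | 31 |
| 0.7 | 0.316 | 0.245 | 0.229 | 1.14 | 35 |
| 0.8 | 0.316 | 0.200 | 0.192 | 1.08 | 37 |

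Change has a larger variance than post-only when 2(1 − ρ) > 1, that is, when ρ < 0.5.

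**Step 4: entry floor.** Suppose the floor multiplies baseline variance by k, with ρ still the correlation before selection. The change variance is then [(1 − ρ²) + k(1 − ρ)²] × 2/n. With k = 0.5 and ρ = 0.3: (0.91 + 0.5 × 0.49)/0.91 × 36/37 = 1.155/0.91 × 36/37 = 1.23. At 0.5, 0.7 and 0.8 the ratio is 1.14, 1.06 and 1.03. This is one illustrative k; stronger selection would give smaller ratios.

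**Step 5: the planning threshold.** The chance that an intervention with no effect shows 0.5 SD or more at a given visit is the upper normal tail at 0.5/SE. For change it is 9.1%, 5.7%, 2.1% and 0.6%; for the adjusted contrast it is 5.1%, 3.6%, 1.4% and 0.5%.

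**Step 6: the SD.** Dividing a difference of 0.5 baseline SDs by the SD of change gives 0.5/√(2(1 − ρ)) = 0.42, 0.50, 0.65 and 0.79. The choice of SD alone can therefore put one result on either side of 0.5.

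**The case against.** **The wording most naturally means a baseline covariate.** One model could take week 8 and month 4 as outcomes, adjust for baseline and read the group difference at each visit. That analysis is sound, and the text does not rule it out. But the plan names group by time, and in such a model that term is the change in the group difference between the two follow-up visits, not the effect at either. The plan also describes the short-term window as starting at baseline. So even on this reading the text needs correcting.

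**A change contrast does use baseline.** This stands. Against ignoring baseline, its variance is 2(1 − ρ) = 0.60 at ρ = 0.7 and 0.40 at ρ = 0.8, a real gain. A reader might infer that the model gets nothing from baseline; that is too strong. The loss is relative to proper adjustment, and relative to post-only just when ρ < 0.5.

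**Standard errors.** A reader might also infer that entering baseline twice makes standard errors too small. That depends on a random-effects structure, a set of visits and a missing-data rate that the plan does not state, so it cannot be held against the plan.

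**Proportion.** This is a 40-family pilot with no stated test or power, and Specific aims says only that a larger study may be proposed. At ρ of 0.7 or 0.8 the differences in Step 5 are under one percentage point. This limits the weight of the point. The plan has only two groups, so the undefined reference to contrasts has no consequence for the group factor. It and the unnamed covariance structure are wording clarifications.

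**Conclusion.** The concern holds in a limited form. In a short-term fit as described, with free baseline means, the group-by-time term does not deliver the baseline control that Aim 2 asks for. Its variance is about 8% to 50% higher than that of an adjusted contrast across assumed correlations of 0.8 down to 0.3, and 3% to 23% higher if the entry floor halves baseline variance. These figures assume complete data and equal follow-up variances; the plan supplies neither a correlation nor a missing-data rate.

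Randomisation keeps the change contrast unbiased, so a reader should not infer that the effect size would be systematically wrong. The cost is extra noise in the number that feeds the planning decision. The missing standardiser is a gap in specification that adds to the uncertainty over what would count as medium. The change is worth making because it costs almost nothing, but it does not threaten the pilot.

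**What to change.** Revise the Aim 2 paragraph to use baseline once, by one of two routes:

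- **Baseline as an outcome with one mean common to both arms.** This keeps every randomised family that has a baseline value, in line with the intent-to-treat statement.
- **Baseline as a covariate, with post-baseline outcomes only.**

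State that baseline gaming does not enter a second time through the covariate clause. Define the effect size as the adjusted group difference, with 95% CI, at end of treatment and at month 4. Report it in raw units and, if it is standardised, by one SD named in advance.

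The baseline SD needs care as the yardstick for medium, because the entry floor may narrow it. With baseline variance halved, 0.5 baseline SDs is 0.5 × √0.5 = 0.354 of the unselected SD. With the adjusted SEs above, an ineffective intervention would reach that by chance in 12.4%, 10.1%, 6.1% and 3.3% of trials.

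For clarity, also name the within-family covariance structure, and define or delete the reference to contrasts.

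The cost is SAP wording and model code, with no new data. One small downside: visit contrasts treat late visits as on schedule unless actual time is also in the model. It can be kept as a covariate or used in a sensitivity analysis.

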Reducing Internet gaming: A pilot psychotherapy development study

NCT02726880

Protocol & Statistical Analysis Plan

IRB Approval Version: 5/9/2020

PROTOCOL: Reducing Internet gaming: A pilot psychotherapy development study

PRINCIPAL INVESTIGATOR: [name].

Abstract

The fifth revision of the Diagnostic and Statistical Manual for Mental Disorders (DSM-5) includes in its research appendix a potential new diagnosis—Internet gaming disorder (IGD). This condition primarily affects adolescent boys and young adult men, who rarely seek treatment on their own. More often, parents express concerns about their child's game playing behaviors. This psychotherapy development study will evaluate feasibility and effect sizes of an intervention designed to help parents reduce their child's gaming problems; the intervention allows for child participation, but it is geared toward parents, regardless of whether or not their child is willing to participate. A total of 40 parents concerned about their child's gaming behaviors will complete self and parental report inventories and structured diagnostic interviews regarding gaming, substance use and psychosocial functioning. Children who elect to participate will complete parallel versions of the instruments. Participants will be randomized to a control condition consisting of referral for mental health issues and family support services or to a 6-week behavioral intervention designed to assist with better monitoring and regulating the child's game playing behaviors. Gaming and other problems will be assessed pre-treatment, at the end of treatment and at a 4-month follow-up. This study will be the first to evaluate the reliability and validity of a parental version of the DSM-5 criteria for IGD in a clinical sample, and it will assess associations of IGD with substance use, mental health conditions, and family functioning as well. This study will be the first randomized trial of an intervention designed to assist parents in reducing their child's gaming problems, and results will help guide future development of interventions for Internet gaming disorder.

Specific aims

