2. To examine the effect size of the intervention for reducing gaming. Parental reports of their child's frequencies and durations of game playing behaviors will be compared over time between conditions to establish effect size estimates.

Exploratory aims are to assess the effect size of the intervention on secondary outcomes, including indices of

substance use, conduct and attention problems, family communication, psychosocial functioning and quality of life. In addition, we will evaluate concordance between parental and child reports on measures of gaming and gaming problems. These data will help inform development of parent assessment tools for IGD.

Results from this pilot trial will be used to guide future grant applications. If data are promising, we will improve and modify the intervention based on parent and child feedback. If medium or larger effect sizes are detected for decreasing gaming or improving psychosocial functioning, a larger scale, longer-term study may be proposed. Even in the absence of treatment-specific effects, these results will provide valuable information about how gaming and psychosocial problems change over time. Given increasing scientific interest in this condition, this study is timely and critical for addressing concerns related to this emerging public health issue.

Background and significance

The vast majority of children, along with many young adults, play video or electronic games. A nationally representative study of US youth between the ages of 8 and 18 found that 88% played games electronically, and 68% played at least weekly and 23% daily (Gentile, 2009). Although most videogame playing is harmless, excessive play can lead to psychosocial and even medical problems, with reports of game-induced seizures and even deaths (Chuang, 2006; BBC News; Reuters). Although very few cases rise to these extremes, governments of some Asian countries have declared excessive game playing to reach near epidemic proportions, and treatment clinics have been established around the world, including the US.

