As in other populations with addictive disorders, few youth or young adults seek treatment on their own (Alegria et al., 2011; Hardoon et al., 2003; SAMHSA 2009ab). More often, parents express concerns about their child's behaviors, and many treatments for IGD include a family component. Therefore, this study will focus on parents, with family sessions involving the youth encouraged but not required. Data suggest that parents can have strong influences on children's game playing. For example, allowing videogame systems in a child's bedroom is associated with more frequent playing (Roberts & Foehr, 2008) and greater use of violent and mature-rated games (Olson et al., 2007). Parental guidelines related to playing time are also inversely associated with excessive game playing. Carlson et al. (2010) surveyed 7,415 youth and their parents and found that youth who reported their parents had specific and well-defined rules regarding playing were less likely to play excessively than those who reported their parents had no such rules; likewise, parents who indicated they had firm limits noted their children were less likely play excessively than parents without clear limits. In addition, frequent monitoring of behaviors is associated with improved outcomes along a number of dimensions (Michie et al., 2012; Steinberg et al., 2013), and this intervention teaches parents to monitor their child's game playing behavior. It will also assist parents in restructuring their home environment to be less conducive toward game playing, and it will provide communication skills training to encourage and set clear expectations about game playing behaviors. Borrowing from effective behaviorally based family based substance abuse interventions for adolescents and young adults (Stanger et al., 2009; Waldron et al., 2007), this behavioral treatment also encourages methods to provide positive contingencies for non-game playing

behaviors. The primary aim of this pilot study is to evaluate the feasibility and effect size of this behavioral intervention for reducing gaming and related problems and improving family functioning.

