Session 5 will continue discussions of rewards for non-gaming playing. Therapists will review rewards provided the prior week, along with suggestions for encouraging and rewarding non-game playing in the future. Communication styles will be reviewed, and the parent (and child, when available) will role play assertive communication skills, especially as relates to game playing.

Session 6 will conclude with a review of progress and a discussion of long-term goals with respect to gaming. The therapist will provide additional recording logs and remind parents to continue monitoring play, offering alternatives to play, and rewarding non-gaming behaviors to prevent relapse.

The six sessions will be scheduled approximately once per week over an 8-week period, allowing for the possibility of some missed or re-scheduled sessions. The goal will be to complete all 6 sessions over 8 weeks; any sessions not completed by week 12 will not be re-scheduled. Study sessions may be completed over the phone or video if needed.

Study visits and follow-up assessments will be scheduled as described above and we have many procedures in place to schedule and complete visits as planned (e.g., collection of contact information, reminder calls and cards, etc.). However, some flexibility is required to protect participants from unnecessarily limiting study procedures to a specific calendar day. If a participant misses an appointment, research staff will attempt to contact and reschedule, but we anticipate late and missed appointments.

Training and therapists: Treatment will be conducted by 2 clinical psychologists. Training and supervision will consist of didactics, role plays and review of audiotapes of role-plays and actual sessions. We will ask all participants to sign a separate consent for audiotaping, although they may participate without allowing taping. Tapes will be reviewed by both therapists and rated for general therapy skills and intended content of the sessions by a modified Yale Adherence Competence Scale (YACS; Carroll et al., 2000). Therapists will begin treating patients once they score good or better on all YACS items on role-plays covering each session. If ratings fall below a mean of good, additional training and supervision will occur.

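### Does the plan need a precision figure and a single named contrast behind its statement that 20 per group is enough to assess effect sizes?

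*Combined protocol and SAP*

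**What the plan says.** The abstract sets the size: "A total of 40 parents concerned about their child's gaming behaviors", randomised to referral or to six sessions of behavioural therapy. At the end of the Treatments section, the aim is put this way: "The primary aim of this pilot study is to evaluate the feasibility and effect size of this behavioral intervention". The sample-size rationale is the Power analyses paragraph: "Twenty subjects per group are sufficient to assess effect sizes, and if medium or larger effect sizes are noted", larger trials will be proposed to evaluate efficacy. Specific aims has a softer form of the same intention: "If medium or larger effect sizes are detected for decreasing gaming or improving psychosocial functioning, a larger scale, longer-term study may be proposed".

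Under Data Analyses, Aim 2, two gaming measures are compared: "parental reports of proportion of days on which their child played games and durations of game playing will be compared between conditions", with control for baseline, using hierarchical linear models. Two periods count: "Both during treatment (baseline to post-treatment) and longer-term (month 4) efficacy will be evaluated". Some loss is expected: "These are continuous measures, with missing data likely". The paragraph on scheduling study visits adds "but we anticipate late and missed appointments". Psychosocial functioning and the other outcomes are labelled exploratory.

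The document gives no alpha, power, SD, target interval width, baseline correlation or attrition rate, and no number for medium.

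**The concern.** There are two worries.

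- **Precision.** Effect size is half of the stated primary aim, so the claim that 20 per group is sufficient carries the whole sample-size rationale, and nothing supports it. At this size a medium estimate is compatible with no effect and with a very large one.
- **Routes to a promising result.** The progression statement names no measure and no time. Either gaming measure at either time could meet it, and in Specific aims so could psychosocial functioning alone. The more routes there are, the more often chance alone yields a medium estimate.

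If both worries were well founded, a grant application could rest on one favourable estimate among several, read as firmer than it is.

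**Working it through.** **Inputs from the plan:** n = 20 per group; two gaming measures; two post-baseline times; baseline adjustment.

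**Assumptions:** medium is d = 0.5; intervals are two-sided 95%; baseline-outcome correlation r is 0.5 to 0.6, with 0.7 as a check; correlation between the two post-baseline times runs from r to 0.7; cross-measure correlation is 0.5 to 0.7 times the within-measure correlation; 16 per group stands for a 20% loss.

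The plan states no figure to reproduce, so the check starts from n = 20.

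**Step 1: interval for an observed d = 0.5.**

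SE = sqrt[(2/n)(1 - r²) + d²/(4n)]

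- Unadjusted: sqrt(0.100 + 0.0031) = 0.321. With 1.96 this gives -0.13 to 1.13; the noncentral t interval agrees to two decimals.
- Adjusted, r = 0.5: sqrt(0.075 + 0.0031) = 0.280. With t on 37 df (2.026) the half-width is 0.566, giving -0.07 to 1.07. Without the d² term it is -0.05 to 1.05.
- Adjusted, r = 0.7, with t: 0.03 to 0.97.
- 16 per group: -0.21 to 1.20 unadjusted (noncentral t); -0.14 to 1.14 at r = 0.5.

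The lower limit reaches zero at r of about 0.63 to 0.65 with 20 per group, and 0.72 to 0.74 with 16. The lower figure of each pair omits the d² term.

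**Step 2: chance of an estimate of 0.5 or more under no effect, one contrast, n = 20.**

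- Unadjusted: 1 - Φ(0.5/sqrt(0.100)) = 1 - Φ(1.58) = 5.7%.
- Adjusted, r = 0.5: 1 - Φ(0.5/sqrt(0.075)) = 1 - Φ(1.83) = 3.4%.

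Simulation with an estimated SD gives about 6% unadjusted, and about 4% (r = 0.5) or 3% (r = 0.6) adjusted.

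**Step 3: at least one of four gaming contrasts, under no effect.** Four independent contrasts would give 1 - (1 - 0.057)⁴ = 21% unadjusted and 1 - (1 - 0.034)⁴ = 13% adjusted at r = 0.5. Simulation with correlated contrasts (20,000 replicates per setting; baseline-adjusted difference divided by the pooled post-baseline SD), n = 20:

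| Analysis | One contrast | Any of four |
|---|---|---|
| Unadjusted | 6% | 15% to 18% |
| Adjusted, r = 0.5 to 0.6 | 3% to 4% | 9% to 13% |
| Adjusted, r = 0.7 | 2% | 6% |

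The ratio is roughly 2 to 3, and lower when the two measures are more closely correlated.

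**Step 4: what one named contrast would cost.** If the true effect is 0.5, a single estimate reaches 0.5 about half the time, whatever the sample size. If the true effect is 0.5 on all four contrasts (n = 20), at least one reaches 0.5 in about 75% to 85% of trials. Naming one contrast therefore cuts a false signal from about 9% to 13% down to 3% to 4%, and a true signal from about 75% to 85% down to 50%.

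**Limit of the check.** The simulation uses a baseline-adjusted comparison at each time as a stand-in for the planned hierarchical model, which uses all available visits and actual assessment times. It shows the order of size, not the exact precision.

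**The case for a change.** The best case for a change is that it asks for wording only. It seeks no power calculation and no extra participants, only the precision behind the plan's own claim of sufficiency, and in an estimation study precision is the natural justification. Baseline adjustment rescues the interval only at a correlation that the plan never states, and even at 0.7 the interval runs from negligible to large. The two statements of intent also differ in firmness: Power analyses commits to a proposal where Specific aims leaves it open. And an exploratory domain can support progression on its own.

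All of this is factually right. What does not follow is that the plan goes wrong if carried out as written. Whether the interval clears zero is a testing standard that this pilot does not adopt. A precision sentence would narrow no interval and alter no estimate. The Power analyses sentence goes on to treat efficacy as a question for later trials, so it does not present a medium estimate as established. The difference in firmness between the two statements is a drafting slip with no analytic effect. Gaming already ranks above the exploratory outcomes through Aim 2, and letting psychosocial benefit also motivate a follow-on trial is a legitimate choice in early development.

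**Conclusion.** No change is called for. The intervals are wide, about ±0.62 to 0.64 unadjusted and ±0.55 to 0.57 at an assumed r = 0.5, and wider with missing data. That is inherent in a 40-parent pilot, and the plan claims nothing narrower. The missing items are a number for medium and intervals beside the estimates. Analysts supply both as a matter of course when they report model-based effect sizes, and neither alters a result.

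The one change that could alter a decision is to tie progression to a single measure at a single time. That is a trade-off rather than a gain. It removes about 5 to 9 percentage points of false promise (from 9% to 13% down to 3% to 4%, adjusted) and gives up about 25 to 35 points of sensitivity to a true effect of 0.5. It also sets aside either month 4 or end of treatment, both of which the plan evaluates, and the psychosocial route that Specific aims allows. When the only consequence is a proposal for a further trial, the choice belongs to the sponsor.

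This rests on medium meaning 0.5, on the assumed correlations, and, for the sensitivity figure, on a true effect of equal size on all four contrasts. Higher correlations shrink both the false-signal excess and the interval; they do not change the conclusion.
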